9.10 Efficacy Analysis

9.10.1 Primary Efficacy

The proportion of subjects with HDSS of 1 or 2 at 4-weeks in subjects randomized to treatment (p_T) will be higher than that in subjects randomized to sham (p_S).

Subjects Included in Analysis: All mITT subjects.

Endpoint(s): The proportion of subjects with HDSS of 1 or 2 at 4 weeks of follow-up.

Hypothesis:

H_0 : The proportion of subjects with HDSS of 1 or 2 at 4-weeks in subjects randomized to treatment (p_T) will be lower than or equal to that in subjects randomized to sham (p_S), $p_T \leq p_S$

H_a : The proportion of subjects with HDSS of 1 or 2 at 4-weeks in subjects randomized to treatment (p_T) will be greater than that in subjects randomized to sham (p_S), $p_T > p_S$

CANDESANT BIOMEDICAL	CLINICAL STUDY PROTOCOL SAHARA STUDY	Document #: CB-CLP-001 Revision: E
-------------------------	---	---------------------------------------

Sample Size Rationale: . The sample size and power calculations for the randomized cohort are based on the company's clinical trial data as well as on published data (Glaser et al., 2012). To account for substantial variability in the proportion of responders across various trials, multiple scenarios were considered.

Per definition of the primary endpoint a responder is a patient with HDSS values of 1 or 2 at 4-weeks post treatment. If proportions of responders in the treated vs. sham arms are 85% vs. 60%, respectively, then using PASS 2019, testing two proportions using the Mantel-Haenszel test, 50 patients per arm will be needed to detect the treatment difference with the 80% power at the 0.05 two-sided significance level. If proportions of responders in the treated vs. sham arms are 73% vs. 44%, then 45 patients per arm will be needed. The evaluable sample size of 50 patients per arm was chosen

Primary Statistical Analysis: The proportion of patients with HDSS of 1 or 2 at 4 weeks post-treatment will be compared between treatment vs. sham using the Cochran-Mantel-Haenszel (CMH) test stratified by baseline HDSS value of 3 vs. 4 in the FAS population. Statistical significance is achieved with two-sided p-value <0.05 equivalent to one-sided p-value < 0.025.

Additional Statistical Analysis: Additional analyses include those summarized in Section 9.7.3 Evaluation for Pooling of Data and Section 9.8 Handling of Missing Data for the Primary Efficacy Endpoint. The primary statistical analysis will be completed in the PP population as well.

An analysis will also be performed using all available time points with complete follow-up at the time of the analysis. A generalized linear mixed model be used to compare the proportion of subjects with HDSS of 1 or 2 between randomized groups over time on study. The dependent variable is HDSS of 1 or 2 (Y/N) with independent variables to include randomized group, follow-up time, baseline HDSS and two-way interaction terms. The covariance structure among the compound symmetric, auto-regressive and unstructured that provides the best model fit by the Schwarz BIC criterion will be used.

A hierarchical stepwise backward elimination technique will be used to reduce the model. The two-way interactions will be reviewed first, the two-way interaction with the largest p-value provided that p-value is greater than 0.05 will be removed from the model and the model refit and process repeated until only two-way interactions with p-values < 0.05 are retained. The main effects for any two-way interactions retained in the model must remain in the model as well as the randomized treatment. With that said, the main effects will be evaluated in the same manner as two-way interactions. This analysis will be repeated in the PP population as well.

CANDESANT BIOMEDICAL	CLINICAL STUDY PROTOCOL SAHARA STUDY	Document #: CB-CLP-001 Revision: E
-------------------------	---	---------------------------------------

9.10.2 Secondary Efficacy

9.10.2.1 Type I Error Control, Additional Claims and Labeling

Should the primary effectiveness endpoint be found to be statistically significant, additional secondary endpoints will be evaluated for inclusion in the labeling for the device including p-values and 95% confidence intervals. The secondary endpoints listed in Section 9.10.2.2 are in priority order and will be evaluated in that order. If statistical significance is achieved for the highest priority endpoint the testing will move to the next highest until either statistical significance is not reached, or the list has ended. This ordered hypothesis approach permits each hypothesis to be evaluated at two sided $\alpha=0.05$ or equivalently one-side $\alpha=0.025$ and controls the study-wide Type I error at 5%.

Secondary endpoints or additional analysis outside of those that do support additional claims are supportive in nature and not intended to support additional claims. Data may be included in labelling per agreement with the FDA and will be limited to summary statistics (e.g. mean, standard deviation, minimum, median, maximum, number and percent) and will not include 95% confidence intervals or p-values. For more information about the secondary endpoint analyses see Section 9.10.2.3 Secondary Objectives.

9.10.2.2 Priority Order and Hypothesis Tests

These hypothesis tests will be evaluated in the FAS population.

1. **To prove that the mean improvement in QoL scale Bother from baseline to 4-weeks is statistically significantly greater in the treatment group as compared to the sham group.**

Hypothesis:

H_0 : The mean improvement in QoL scale Bother from baseline to 4-weeks in subjects randomized to treatment (μ_T) will be lower than or equal to that in subjects randomized to sham (μ_S), $\mu_T \leq \mu_S$.

H_a : The mean improvement in QoL scale Bother from baseline to 4-weeks in subjects randomized to treatment (μ_T) will be greater than that in subjects randomized to sham (μ_S), $\mu_T > \mu_S$.

Success is defined as a statistically significant difference (at the 0.05 two-sided significance level) between least squared means for randomized groups.

2. **To prove that the mean improvement in QoL scale Impact from baseline to 4-weeks is statistically significantly greater in the treatment group as compared to the sham group.**

CANDESANT BIOMEDICAL	CLINICAL STUDY PROTOCOL SAHARA STUDY	Document #: CB-CLP-001 Revision: E
-------------------------	---	---------------------------------------

Hypothesis:

H_0 : The mean improvement in QoL scale Impact from baseline to 4-weeks in subjects randomized to treatment (μ_T) will be lower than or equal to that in subjects randomized to sham (μ_S), $\mu_T \leq \mu_S$

H_a : The mean improvement in QoL scale Impact from baseline to 4-weeks in subjects randomized to treatment (μ_T) will be greater than that in subjects randomized to sham (μ_S), $\mu_T > \mu_S$

Success is defined as a statistically significant difference (at the 0.05 two-sided significance level) between least squared means for randomized groups.

3. **To prove that the proportion of patients with improvement of at least 2 grades from baseline to 4-weeks in HDSS is statistically significantly greater in the treatment group as compared to the sham group.**

Hypothesis:

H_0 : The proportion of subjects with improvement of at least 2 grades from baseline to 4 weeks in HDSS in subjects randomized to treatment (p_T) will be lower than or equal to that in subjects randomized to sham (p_S), $p_T \leq p_S$

H_a : The proportion of subjects with improvement of at least 2 grades from baseline to 4 weeks in HDSS in subjects randomized to treatment (p_T) will be greater than that in subjects randomized to sham (p_S), $p_T > p_S$

Success is defined as a statistically significant difference (at the 0.05 two-sided significance level) between proportions of patients with at least 2 grade improvement in HDSS from baseline to 4 weeks between randomized group using CMH test stratified by baseline HDSS (3 vs. 4).

4. **Proportion of subjects with at least 50% improvement in gravimetric sweat production (GSP) in subjects treated with the N-SWEAT Patch only at 4-weeks. (GSP will be calculated based on the total sweat produced by both axillae.)**

H_0 : The proportion of subjects with at least 50% improvement in gravimetric sweat production (GSP) in subjects randomized to treatment (p_T) is not statistically significantly different from 0, $p_T = 0$.

H_a : The proportion of subjects with at least 50% improvement in gravimetric sweat production (GSP) in subjects randomized to treatment (p_T) is statistically significantly different from 0, $p_T \neq 0$. Success is defined as a statistically significant result (at the 0.05 two-sided significance level). It is expected that at least 50% of subjects will have at least 50% improvement in gravimetric sweat production from baseline at 4-weeks.

CANDESANT BIOMEDICAL	CLINICAL STUDY PROTOCOL SAHARA STUDY	Document #: CB-CLP-001 Revision: E
-------------------------	---	---------------------------------------

9.10.2.3 Secondary Objectives

9.10.2.3.1 *To compare the mean improvement over baseline for QOL scale Bother between subjects randomized to treatment as compared to sham*

Subjects Included in Analysis: All FAS subjects will be included in the analysis.

Endpoint(s): QOL scale Bother score

Statistical Analysis: An analysis will be performed using all available time points with complete follow-up at the time of the analysis. A generalized linear mixed model be used to compare average change in QOL Bother from baseline to follow-up between randomized groups over time on study. The dependent variable change in QOL Bother from baseline to follow-up with independent variables to include randomized group, follow-up time, baseline HDSS and two-way interaction terms. The covariance structure among the compound symmetric, auto-regressive and unstructured that provides the best model fit by the Schwarz BIC criterion will be chosen.

A hierarchical stepwise backward elimination technique will be used to reduce the model. The two-way interactions will be reviewed first, the two-way interaction with the largest p-value provided that p-value is greater than 0.05 will be removed from the model and the model refit and repeated until only two-way interactions with p-values < 0.05 are retained. The main effects for any two-way interaction retained in the model must remain in the model as well as the randomized treatment. That being said, the main effects will be evaluated in the same manner as the two-way interaction terms. This analysis will be repeated in the PP population.

9.10.2.3.2 *To compare the mean improvement over baseline for QOL scale Impact between subjects randomized to treatment as compared to sham*

Subjects Included in Analysis: All FAS subjects will be included in the analysis.

Endpoint(s): QOL scale Impact score

Statistical Analysis: An analysis may also be performed using all available time points with complete follow-up at the time of the analysis. A generalized linear mixed model be used to compare average change in QOL Impact from baseline to follow-up between randomized groups over time on study. The dependent variable change in QOL Impact from baseline to follow-up with independent variables to include randomized group, follow-up time, baseline HDSS and two-way interaction terms. The covariance structure among the compound symmetric, auto-regressive and unstructured that provides the best model fit by the Schwarz BIC criterion will be chosen.

A hierarchical stepwise backward elimination technique will be used to reduce the model. The two-way interactions will be reviewed first, the two-way interaction with the largest p-value provided that p-value is greater than 0.05 will be removed from the model and the model refit and repeated until only two-way interactions with p-values < 0.05 are retained. The main effects for any two-way interaction retained in the model must remain in the model as well as the randomized treatment. That being said, the

CANDESANT BIOMEDICAL	CLINICAL STUDY PROTOCOL SAHARA STUDY	Document #: CB-CLP-001 Revision: E
-------------------------	---	---------------------------------------

main effects will be evaluated in the same manner. This analysis will be completed in the PP population as well.

9.10.2.3.3 *To compare the proportion of patients with at least a 2 grade improvement in HDSS from baseline between subjects randomized to treatment as compared to sham*

Subjects Included in Analysis: All FAS subjects will be included in the analysis.

Endpoint(s): HDSS.

Statistical Analysis: The proportion of patients with at least a 2 grade improvement in HDSS from baseline to 4 weeks will be compared between treatment vs. sham using the Cochran-Mantel-Haenszel (CMH) test stratified by baseline HDSS value of 3 vs. 4 in the FAS population. Statistical significance is achieved with two-sided p-value <0.05 equivalent to one-sided p-value < 0.025. This analysis will be completed in the PP group as well.

An analysis will be performed using all available time points with complete follow-up at the time of the analysis. A generalized linear mixed model will be used to compare the proportion of subjects with at least 2 grade improvement from baseline to 4 weeks between randomized groups over time on study. The dependent variable is 2 grade improvement over baseline (Y/N) with independent variables to include randomized group, follow-up time, baseline HDSS and two-way interaction terms. The covariance structure among the compound symmetric, auto-regressive and unstructured that provides the best model fit by the Schwarz BIC criterion will be chosen.

A hierarchical stepwise backward elimination technique will be used to reduce the model. The two-way interactions will be reviewed first, the two-way interaction with the largest p-value provided that p-value is greater than 0.05 will be removed from the model and the model refit and repeated until only two-way interactions with p-values < 0.05 are retained. The main effects for any two-way interaction retained in the model must remain in the model as well as the randomized treatment. That being said, the main effects will be evaluated in the same manner as the two-way interactions. This analysis will be completed in the PP group as well.

9.10.2.3.4 *To estimate the proportion of subjects randomized to treatment with at least 50% improvement from baseline to 4 weeks in gravimetric sweat production (GSP)*

Subjects Included in Analysis: All FAS subjects randomized to receive the N-SWEAT patch.

Endpoint(s): The average of 2 accurate GSP measurements will be conducted for each Axilla at each time point. The total sweat production at each timepoint will be calculated by summing the average sweat production from both axilla. The percentage change at 4 weeks will be calculated based on the total sweat production at baseline and 4 weeks.

CANDESANT BIOMEDICAL	CLINICAL STUDY PROTOCOL SAHARA STUDY	Document #: CB-CLP-001 Revision: E
-------------------------	---	---------------------------------------

Statistical Analysis: The potential confounding factors of room temperature, position during evaluation and time of evaluation will be summarized for baseline and 4 weeks. The difference in temperature, time of evaluation and whether or not the baseline and 4 week evaluation were performed in the same or different position will be summarized. These factors will be evaluated with respect to their relationship with the endpoint and association with outlying values, if any, using graphical techniques and summary statistics. Depending on this evaluation, outlying values may be excluded from the analysis with justification provided and relationships, if any found, will be summarized.

The proportion of patients with 50% or greater improvement in percentage change from baseline to 4 weeks will be statistically compared to zero by calculating the Wilson's 95% two-sided confidence interval and comparing the lower bound to zero. If the lower bound is greater than zero, there is statistically significant evidence that the proportion of subjects with a clinically relevant improvement exists and is greater than 0. This analysis will be completed in the PP population as well.

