7. SUBJECT POPULATION

7.1 Population Overview

Healthy male and female subjects in good general health who sweat excessively in the axillae and/or who have primary axillary focal hyperhidrosis, defined as subjects with HDSS score of 3 or 4, will be considered for study participation.

The first 10 subjects will be treated with the N-SWEAT Patch and enrolled into the Roll-In Cohort. Subsequently, subjects will be enrolled into the Randomized Cohort and will be randomized for bilateral treatment with either the N-SWEAT Patch or the Sham control patch.

Subjects enrolled in the study will agree to refrain from the use of over-the counter antiperspirants and the use of any topical steroids or any systemic treatment that may impact their hyperhidrosis symptoms during their participation in this study. Subjects will also be required to have axillary hair clipped or shaven prior to GSP assessments at the screening and the 4-week visits.

Subjects will be asked to keep a daily written dairy for the first 4 weeks and to answer weekly surveys related to their axillary sweating; including the HDSS survey and the Quality of Life surveys (QOL-7, QoL-Impact, Bother, etc) using electronic means (i.e. their cell phone, tablet or computer).

The subject will also be required to report for study visits including screening, baseline (on the day of treatment), 2-3 days after treatment, and a 4-week post treatment follow-up visit. Additional visits at 6-, 8-, 10-, and 12-weeks are recommended to take place in person but may be conducted by phone if an office visit is not possible or practical.

Ten (10) subjects will be included in the Roll-In Cohort at 1 study site and up to 110 subjects will be included in the Randomized Cohort at up to 14 study sites. At least 50 subjects randomized to each group must undergo the assigned treatment. Up to 10 additional subjects may be randomized to account for loss to follow up or other missing and critical data.

Candesant intends to enroll a population with demographics representative of the US. Enrollment will be observed to ensure that at least 20% of subjects are Fitzpatrick Skin Types IV through VI and that 10-15% of subjects are Fitzpatrick Skin Types V and VI.

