8.5 Randomization Cohort

8.5.1 Randomization Process

Note: Randomization should take place immediately before treatment. If a subject meets all eligibility criteria at the screening and baseline visits; but is unable or unwilling to undergo treatment. Do not randomize. The subject should report back for randomization at the time of their planned treatment. If it is more than 7 days

CANDESANT BIOMEDICAL	CLINICAL STUDY PROTOCOL SAHARA STUDY	Document #: CB-CLP-001 Revision: E
-------------------------	---	---------------------------------------

between the qualifying baseline visit and randomization; the HDSS and the physical exam should be repeated to confirm eligibility prior to Randomization.

Randomization will be performed using an electronic system. Upon entering the subject information, the electronic system will assign a unique treatment to the subject. The subject must be treated with the assigned treatment number. In the event that the site is prevented from using the assigned treatment number (either due to the patch being missing, damaged or otherwise unusable) the site must contact the sponsor to receive an alternate treatment number assignment. A contact list will be provided for this purpose.

Subjects will be randomized 1:1 to either an active study N-SWEAT Patch (Treatment) or a sham patch (Sham). There will be no procedural difference between the Treatment Arm and the Sham Arm. The randomization will be stratified by HDSS 3 vs. 4 at baseline and blocked by investigational center. Within each HDSS stratum, block randomization with a randomly selected block size will be used. Up to 110 subjects will be randomized. At least 50 subjects randomized to each group must be evaluable for the primary efficacy endpoint. Up to 10 additional subjects may be enrolled to account for loss to follow up or other missing and critical data.

Crossovers are not permitted by this protocol. Subjects may only receive the N-SWEAT Patch if they are randomized to do so.

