9.7.3 Evaluation for Pooling

Pooling of the investigational sites will be evaluated for the primary efficacy endpoint. Investigational centers with less than 10 randomized subjects will be combined for this purpose. The Breslow-Day test will be used to assess the treatment by site interaction and if statistically significant at $p<0.15$, an overall response rate will be evaluated at 4-weeks using CMH test stratified by site. If not statistically significant, the data will be pooled for analysis.

CANDESANT BIOMEDICAL	CLINICAL STUDY PROTOCOL SAHARA STUDY	Document #: CB-CLP-001 Revision: E
-------------------------	---	---------------------------------------

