1. STATISTICAL CONSIDERATIONS AND GENERAL STATISTICAL ANALYSIS METHODS

This Statistical Analysis Plan (SAP) presents a detailed description of the statistical methods and procedures to be implemented for data analysis in the study and supersedes analyses described in the clinical investigation plan, entitled “An Evaluation of the Safety and Effectiveness of the N-SWEAT Patch for the Treatment of Primary Axillary Hyperhidrosis or Excessive Axillary Sweating (SAHARA)”. Deviations from this plan will be considered only if there is statistical justification. Any deviations from this SAP will be substantiated by sound rationale and documented in the clinical report.

This SAP also provides the analysis plan for “The pH SUB-STUDY – An Evaluation of Skin pH for a Subset of Subjects Treated in the Sahara Study”. The analysis identified for the sub-study is described in Section 13.

Categorical variables will be summarized by counts and percentages. Continuous variables will be summarized by n, mean, standard deviation, minimum, median and maximum.

When the arithmetic mean is found not to be an appropriate measure of central tendency, alternative statistics will be considered (e.g. median). When the distribution of a variable does not support the use of parametric statistics, nonparametric approaches or data transformations may be implemented. If data transformations are used, they will be specified in the final clinical report.

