2. STUDY DESIGN, RANDOMIZATION AND BLINDING

The Sahara Study is a prospective, multi-center, randomized, blinded, pivotal study to evaluate the safety and effectiveness of the N-SWEAT Patch.

Subjects with primary axillary hyperhidrosis or excessive sweating (defined by a score of 3 or 4 on the HDSS), who have provided informed consent and have met the study eligibility criteria, will participate. Up to 120 adult subjects will be enrolled. The first 10 subjects will be treated with the N-SWEAT patch and constitute the roll-in cohort and up to 110 subjects will be randomized to 1 of 2 treatment groups in a 1:1 ratio to receive a single administration of the N-SWEAT Patch or a sham control patch. The randomization will be blocked by investigational center and stratified by HDSS 3 vs. 4 at baseline. Although a sample size of 100 subjects (50 in each group) is the target; up to 10 additional subjects may be enrolled to account for loss to follow up or other missing and critical data.

Randomized subjects will be blinded to their treatment assignment. Site personnel administering the treatment will observe the treatment effect and the disposal process and may be unblinded as a result of their observations. This person will not conduct the follow-up assessments and will not reveal the assumed treatment assignment to the subject, other site personnel, or the investigator at any time during the study follow-up period. Study subjects and study staff will be instructed not to discuss assumptions about the treatment received.

The sponsor will identify those who need to be unblinded in order to conduct the study. All others at the sponsor will remain blinded until the 4 week analysis.

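### Randomisation is blocked by centre, but the Bother and Impact change models leave centre out; if blocks are formed within centre, this forgoes some attainable power on the first two gatekept secondary endpoints.

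*Protocol*

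**What the plan says.** **Randomisation.** Protocol 8.5.1: "The randomization will be stratified by HDSS 3 vs. 4 at baseline and blocked by investigational center". SAP 2 agrees: "The randomization will be blocked by investigational center and stratified by HDSS 3 vs. 4 at baseline"; Protocol 9.2 says the same. Protocol 8.5.1 then adds that, inside each HDSS stratum, "block randomization with a randomly selected block size will be used", without giving the sizes. Protocol 7.1: "up to 110 subjects will be included in the Randomized Cohort at up to 14 study sites".

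**Bother and Impact models.** The outcome is change from baseline, modelled "with independent variables to include randomized group, follow-up time, baseline HDSS and two-way interaction terms" (Protocol 9.10.2.3.1 and 9.10.2.3.2). The SAP, which "supersedes analyses described in the clinical investigation plan", uses the same list in 11.2.3.1 and 11.2.3.2. Neither document includes a fixed or random centre term.

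**Where centre does appear.** Protocol 9.7.3: "Pooling of the investigational sites will be evaluated for the primary efficacy endpoint". SAP 8.3 has the same limit to the primary endpoint. The covariate rule in Protocol 9.7.1 and SAP 8.1 is triggered by baseline characteristics that differ between the arms, and centre is not among those listed.

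**Gatekeeping.** Bother is tested first and Impact second, each at two-sided 0.05. Passing permits p-values and 95% confidence intervals in the labelling; a miss ends formal testing down the list (Protocol 9.10.2.1 and 9.10.2.2; SAP 11.2.1 and 11.2.2).

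**The concern.** Two factors shape the allocation, baseline HDSS and centre, and the models carry only the first. When arms are balanced within centre, differences between centres largely cancel out of the treatment comparison. A model that does not know about centre still counts those differences as residual variation between subjects, so it reports a standard error larger than the design warrants. The covariance structures to be compared by BIC do not repair this. As ordinarily applied they describe repeated measurements on one subject, whereas a centre effect links different subjects.

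At stake are the width of the intervals that may go into the labelling and the chance of passing Bother and Impact. Failing either one also closes off the 2-grade HDSS endpoint and the GSP endpoint. The sample size is driven by the primary endpoint alone (Protocol 9.3; SAP 4), so the documents do not show how much power these two endpoints have.

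**Working it through.** **1. The plan's own figure.** It concerns the primary endpoint only (Protocol 9.10.1; SAP 11.1). With n = [1.96 sqrt(2 p q) + 0.8416 sqrt(p1 q1 + p2 q2)]^2 / (p1 - p2)^2, where p is the mean of p1 and p2, each q is 1 minus its p, and there is no continuity correction:

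- 85% vs 60%: (1.2377 + 0.5102)^2 / 0.0625 = 48.9, so 49 per arm (plan: 50).
- 73% vs 44%: (1.3657 + 0.5605)^2 / 0.0841 = 44.1, so 45 per arm (plan: 45).

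The plan's figures are reproduced. No effect, SD, power or centre share is given for Bother or Impact, so everything below rests on assumed values.

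**2. Formula under full balance within centre.** Take total SD 1 and 50 evaluable per arm, so the model SE without centre is sqrt(2/50) = 0.2. Take the effect that gives 80% power at that SE: d = (1.960 + 0.8416) x 0.2 = 0.56. Let s be the share of variance in the change score that lies between centres.

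- Model SE / true SE = 1/sqrt(1 - s)
- Power without centre = Phi((d/0.2 - 1.96)/sqrt(1 - s))
- Power with centre = Phi(d/(0.2 sqrt(1 - s)) - 1.96)
- Type I error without centre = 2[1 - Phi(1.96/sqrt(1 - s))]

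| s | SE too wide by | Power without | Power with | Type I without |
|---|---|---|---|---|
| 0 | 0% | 80.0% | 80.0% | 5.0% |
| 5% | 2.6% | 80.6% | 82.0% | 4.4% |
| 10% | 5.4% | 81.3% | 84.0% | 3.9% |
| 20% | 11.8% | 82.7% | 88.0% | 2.8% |

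Example at s = 10%: 0.8416/0.9487 = 0.887, so power is 81.3% without centre; 2.8016/0.9487 - 1.96 = 0.993, so 84.0% with it.

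**3. Simulation with realistic imbalance.** Full balance is optimistic: 110/14 is about 8 subjects per centre, or about 4 per centre-by-HDSS cell, so many blocks stay incomplete. Three simulations used 14 unequal centres, blocks of 2 or 4 within centre by HDSS, a single 4-week contrast and total SD 1. Power without centre, then with a random centre intercept:

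| s | 110 subjects, d = 0.54, 4,500 runs | 100 subjects, d = 0.56 | 100 subjects, d = 0.56, 3,000 runs |
|---|---|---|---|
| 5% | 80.7 / 82.2 | 79.2 / 80.3 | 79.2 / 80.5 |
| 10% | 81.8 / 84.2 | 80.7 / 83.1 | 80.6 / 83.1 |
| 20% | 82.4 / 87.3 | 81.7 / 86.3 | 82.0 / 86.7 |

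- Gains are 1.1 to 1.5, 2.4 to 2.5 and 4.6 to 4.9 points. With 7 centres instead of 14, the second simulation gave 1.1, 2.4 and 5.7 points.
- At s = 0 the first simulation gave 79.3% vs 79.8%, so essentially nothing changes.
- Null rejection without centre in the third simulation was 4.8%, 4.1% and 3.0% at s = 5%, 10% and 20%; with the intercept it was 5.1%, 5.0% and 4.7%.
- At s = 20% under the null, the second simulation's mean model SE without centre was 0.198 against a true SD of 0.182. The ratio is 1.09, below the 1.118 of full balance.

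**4. Fixed centre effects.** In the second simulation these gave 78.2% at s = 5% (79.2% without centre), 81.7% at 10% and 84.9% at 20%. At low shares there is no gain.

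**5. If blocks run only within HDSS strata.** At s = 10% the model SE without centre matched the true one (0.198 vs 0.198) and null rejection was 5.0%. A random intercept still raised power from 79.1% to 80.8% at 10% and from 79.7% to 84.3% at 20%, as ordinary covariate adjustment would.

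**The case against.** - **The outcome is a change score.** A stable difference between centres in how subjects score themselves is subtracted out before modelling. Only differences in mean improvement remain, and nothing in the documents indicates their size. The items are self-completed, electronically where possible, so site raters add little. This stands: shares of 10% and 20% are assumptions, and a small share is quite possible.
- **Blocking within centre is one reading.** The sentence on random block sizes in Protocol 8.5.1 refers to HDSS strata, and the synopsis names only HDSS stratification. A reader might infer that the standard errors are too wide whenever centres differ. The documents do not support that without condition. Protocol 8.5.1, Protocol 9.2 and SAP 2 all say blocked by centre, which favours the reading used here without settling it.
- **Power is not eroded.** At fixed total variance, power without centre rises slightly with s (79.3% to 82.4% in the first simulation). What is lost is a further gain. This stands.
- **The simulated analysis is simpler than the planned one.** None of the simulations fitted the full repeated-measures model with BIC selection and backward elimination, and Kenward-Roger was not shown to have been used. A normal reference instead of t adds about 0.4 to 0.6 points of power, so some gains may be slightly flattered. A separate run with a t reference still gave about 1.3 points at s = 5%.
- **The model list may not be exhaustive.** Its wording leaves room for other terms, but no section of either document adds centre.

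**Conclusion.** The point holds as an efficiency improvement. The plan randomises by centre and does not analyse Bother and Impact by it. If blocks are formed within centre and mean improvement differs between centres, the standard errors are somewhat too wide and the tests conservative. The power forgone is about 0 to 1.5 points at a between-centre share of 5% or less, about 2 to 2.5 points at 10%, and about 4 to 5 points at 20% with 14 centres. These sizes rest on an assumed share, effect and block size, none of which the documents state.

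Two stronger conclusions that a reader might draw are not supported. The error rate is not inflated: rejection under the null is at or below 5%, so the omission cannot produce a false label claim. Nor is a power target missed, because the documents set none for Bother or Impact.

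**What to change.** In Protocol 9.10.2.3.1 and 9.10.2.3.2 and SAP 11.2.3.1 and 11.2.3.2, add a random intercept for investigational centre to the Bother and Impact models. Exempt it from backward elimination and specify Kenward-Roger degrees of freedom. Do not use fixed effects for up to 14 small centres. State in Protocol 8.5.1 whether blocks are formed within centre by HDSS or within HDSS only.

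Leave the primary CMH test stratified by HDSS, because HDSS-by-centre strata would be sparse. Leave the supporting binary HDSS mixed models unchanged as well: the effect of the term there was not computed, and it would turn the odds ratio into a centre-conditional one.

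The cost is a short wording change, to be made before the sponsor is unblinded at the 4-week analysis (SAP 7). The downside is one more variance component, which may be estimated as zero and then changes essentially nothing.
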